2.0 TRIAL DESIGN

[figure not shown]
Open label phase I trial. Primary objective is to determine the recommended phase 2 dose (RP2D) of the combination of spartalizumab and siltuximab. The design is 3+3 with 3 dose levels of siltuximab. Maximal Tolerated Dose (MTD) is defined as the dose at which less than one-third of the subjects experience a DLT in the first 6 weeks of treatment.

After determining the RP2D, an additional 24 patients with pancreatic cancer will be enrolled in an expansion phase to confirm toxicity profile and obtain paired biopsies. Paired biopsy performed on all patients in each group. Patient must have a primary or metastatic non-bone

Protocol/Version No.: 5, Date December 15, 2022

site that is amenable to safe biopsy. Bone only lesions are not suitable for biopsy. Investigators will discuss with radiologist each case to ensure safety of biopsy procedure.

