6.2.1 Siltuximab dose levels

Open label phase I trial. Primary objective is to determine the recommended phase 2 dose (RP2D) of the combination of siltuximab plus spartalizumab in a pancreatic cancer. The design is 3+3 with 3 dose levels of siltuximab.

Tuble 6. Dose esculation for shitaximae					
No of pts	Cohort Level	Siltuximab	Spartalizumab		
3 to 6	1	6 mg/Kg IV every 3 weeks	300 mg every 3 weeks		
3 to 6	2	11 mg/Kg every 3 weeks	300 mg every 3 weeks		
3 to 6	2a	9 mg/Kg every 3 weeks	300 mg every 3 weeks		

Table 6. Dose escalation for siltuximab

Dose level 2a will only be tested if we observe 2 DLT's on dose level 2.

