6.2.2 Dose Escalation

For the purposes of dose escalation decisions, each cohort will consist of 3 to 6 newly enrolled patients who will be treated at the specified dose level. The first cohort will be treated with the starting dose of 300 mg of spartalizumab and 6 mg/Kg of Siltuximab.

Patient will be considered evaluable for dose escalation decision if patients have received at least 2 infusions of both study drugs (spartalizumab and siltuximab) and had safety assessments for a minimum of 6 weeks or have had a DLT during the first 6 weeks. Dose escalation decisions will occur when the cohort of patients has met these criteria. All patients within a dosing cohort must have completed the DLT evaluation period and have been evaluated for DLT prior to dose escalation.

If 1 of the first 3 patients develops a DLT, then enroll up to 3 additional patients at the same dose level. If 2 or more patients in any dose cohort of 6 or fewer patients have a DLT, then the MTD of the combination is exceeded. If there are no DLTs in the first 3 patients at dose level 1 or 1 of 6 patients in dose level 1 has a DLT, enroll 3 patients into the 11 mg/Kg dose level. If 2 or more patients in this dose cohort have a DLT, reduce dose to 9 mg/Kg and enroll 3 more patients. If an acceptable dose is identified, then start the expansion phase. Prior to dose escalation, we will obtain approval from the Data Safety and Monitoring Committee (DSMC) for implementation of dose escalation decisions.

Protocol/Version No.: 5, Date December 15, 2022

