This is a 3+3 standard phase I trial design. The plan is to evaluate two dose cohorts- 6 mg/Kg and 11 mg/Kg of siltuximab. An intermediate dose cohort (9 mg/Kg) will be evaluated only if we observe 2 or more DLT's in the 3 or 6 patients enrolled on the 11 mg/kg dose. If we observe 2 dose limiting toxicities on dose level 1, then the study will be completed with three patients (minimal number of patients). If we observe two DLT in the first three patients on dose level 1, the study will stop and the principal investigator will discuss at that point whether a lower dose level of siltuximab should be tested. If we do not observe any dose limiting toxicities the study will require 9 patients. If we observe one dose limiting toxicity per dose level (maximum number of patient), then the study would require 18 patients. Therefore the phase part sample size can range from 3 to 18 patients.

Expansion phase will be started once the recommended phase II dose (RP2D) is determined. Given minimal activity of checkpoint inhibitors in pancreatic cancer (Response rate less than 5%), an overall response rate of the combination of PD-1 plus IL-6 inhibitor of 20% would be considered clinically significant. With an alpha of 0.1, and power of 90% a total of 24 patients should be sufficient to make this determination. We will also obtain biologic endpoints with the paired biopsy samples that can help further develop the combination and understand its role in pancreatic cancers. We plan to enroll 24 patients on the RP2D level. Patients in the expansion phase will be assigned to treatment arms by PI (spartalizumab or spartalizumab plus siltuximab). After the first 3 weeks all patients will receive the combination therapy. There is no planned comparison between the two arms. The aim of the expansion phase is to confirm the safety profile and tolerability of the regimen in patients with pancreatic cancer.

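### Section 12.1's 9 patients for no DLT, its scenario for 18, and the minimum total of 27 do not follow from the escalation rules as written

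*Combined protocol and SAP*

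**What the plan says.** **Escalation rules.** Section 6.2.1 (like section 2.0) states "The design is 3+3 with 3 dose levels of siltuximab", with 3 to 6 patients each at 6 mg/kg (level 1), 11 mg/kg (level 2) and 9 mg/kg (level 2a). It adds "Dose level 2a will only be tested if we observe 2 DLT's on dose level 2". Section 6.2.2 enlarges a cohort in one circumstance: "If 1 of the first 3 patients develops a DLT, then enroll up to 3 additional patients at the same dose level". Two or more DLTs in a cohort of up to six mean that the MTD is exceeded. After 0 of 3 or 1 of 6 at level 1, the instruction is "enroll 3 patients into the 11 mg/Kg dose level". Escalation ends with "If an acceptable dose is identified, then start the expansion phase".

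**Sample size.** Section 12.1 describes the levels differently: "The plan is to evaluate two dose cohorts- 6 mg/Kg and 11 mg/Kg of siltuximab", with 9 mg/kg conditional on two or more DLTs at 11 mg/kg. It then gives these escalation numbers:

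- Two DLTs at level 1: 3 patients, and the study stops.
- No DLT: "If we do not observe any dose limiting toxicities the study will require 9 patients".
- One DLT per dose level: 18, labelled as the maximum.
- Overall range: 3 to 18.

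Section 2.0 says that once the RP2D is known, "an additional 24 patients with pancreatic cancer will be enrolled in an expansion phase". Section 12.1 and the Trial Summary (section 1.0) both give the total treated as 27 to 42, with up to 70 enrolled to allow for screen failures.

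**The concern.** The no-DLT figure, the scenario for 18 and the lower end of the total all conflict with the rules that are meant to generate them. The conflict over level 2a lies within section 12.1 itself.

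Readers who approve or oversee the trial take the numbers to be treated from this section and the synopsis. The figure of 9 also leaves a question open: is a clean first cohort of three at 11 mg/kg enough to start the expansion, or were more patients intended there?

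**Working it through.** **Where the plan's figures come from.** 27 = 3 + 24 and 42 = 18 + 24, so the total is the 3 to 18 escalation range plus the expansion.

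**Outcomes at one level (6.2.2):**

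| DLTs | Patients | Result |
|---|---|---|
| 0 of first 3 | 3 | acceptable |
| 1 of first 3, then 0 of next 3 | 6 | acceptable |
| 1 of first 3, then 1 or more of next 3 | 6 | exceeded |
| 2 or 3 of first 3 | 3 | exceeded |

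**Chaining the levels.** Level 2 opens only if level 1 is acceptable; level 2a opens only if level 2 is exceeded.

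| Path | Escalation patients | Plus 24 if an RP2D is found |
|---|---|---|
| Level 1 exceeded, study stops | 3 or 6 | none |
| Level 2 acceptable | 6, 9 or 12 | 30, 33 or 36 |
| Level 2 exceeded, level 2a opened | 9, 12, 15 or 18 | 33, 36, 39 or 42 |

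**(a) No DLT.** One path exists: 0/3 at level 1, 0/3 at level 2. 3 + 3 = 6, against the stated 9. Every path that uses 9 escalation patients contains at least one DLT.

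**(b) One DLT at each opened level.** Level 1 at 1/6 leads to level 2. Level 2 at 1/6 is acceptable, so level 2a stays closed. 6 + 6 = 12, against the stated 18. Reaching 18 needs level 1 at 1/6, level 2 at 1/3 and then filled to six with at least two DLTs in all, and level 2a at 1/3 and filled to six. That is at least 1 + 2 + 1 = 4 DLTs.

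**(c) Minimum total.** The 3-patient path ends with level 1 exceeded. Section 12.1 stops the study there and opens the expansion only once an RP2D exists, so 24 cannot be added to that 3. The smallest path that yields an RP2D uses 6 patients: 6 + 24 = 30, against the stated 27.

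**Can another reading rescue the figures?**

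| Reading | No DLT | One DLT per level | Total with expansion |
|---|---|---|---|
| Stated in 12.1 | 9 | 18 | 27 to 42 |
| Rules as written | 6 | 12 | 30 to 42 |
| Six patients required at the declared dose | 3 + 6 = 9 | 12 | 33 to 42 |
| All three levels always opened | 3 × 3 = 9 | 3 × 6 = 18 | minimum 9 + 24 = 33 |
| RP2D-level escalation patients counted inside the 24 | 6 | 12 | 27 to 36 |

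No row reproduces 9, 18 and 27 to 42 together. The fourth reading also contradicts the condition on level 2a, and the fifth contradicts section 2.0, where the 24 are additional.

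**Sensitivity.** Section 6.2.2 allows up to three extra patients, so a level might close at its second DLT with 4 or 5 treated. That shortens only exceeded levels and leaves 6, 12, 30, 18 and 42 unchanged.

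**The case against.** **18 is a correct bound.** Section 12.1 labels it as the maximum, and it is. A reader might infer that 18 should be replaced by 12. The rules do not support that: 12 answers a different question, and only the path described for 18 is wrong. This objection stands.

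**The 9 may be deliberate.** Section 6.2.2 spells out acceptance for level 1 but never says in terms that 0 of 3 at 11 mg/kg is enough to declare the RP2D. The MTD definition in section 2.0 sets no minimum number of patients. Requiring six at the declared dose gives exactly 9. This stands in part: 6 is what the written enlargement rule gives, but intent cannot be settled from the text. It is tempting to conclude that level 2a was simply counted unconditionally, since 3 × 3 = 9 and 3 × 6 = 18. The documents do not show that either. Even with six at the declared dose, the scenario for 18 and the 27 still fail.

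**30 is conditional.** It is not a floor on the number treated. A stop at level 1 treats 3 to 6, and the safety halt in section 12.1 could end the expansion before 24. This stands.

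**Treated and evaluable patients differ.** The total counts patients treated. Section 6.7.1 lets non-evaluable escalation patients be supplemented, so more could be treated than the path counts show. It provides no replacements in the expansion, and section 12.3 makes patients below 80% of the prescribed dose in-evaluable for toxicity. The corrected total should therefore not be called a number of evaluable patients. This stands.

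**The matter is editorial.** It is true that no escalation, stopping or analysis rule uses these figures. They are nevertheless what the sample-size section exists to state, and one is repeated in the synopsis.

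**Conclusion.** The concern holds as an inconsistency between the written escalation rules and the numbers in section 12.1, carried into the synopsis for the total:

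- **No DLT:** 9 stated, 6 under the rules as written.
- **One DLT per opened level:** 18 stated, 12 derived. 18 remains the correct maximum, reached by a different path.
- **Minimum total:** 27 stated, 30 derived, given an RP2D and a completed expansion of 24 patients additional to escalation.

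These results assume that a cohort grows only after one DLT in its first three, and that an acceptable result at level 2 leads straight to expansion. The path counts are before any supplementation under section 6.7.1.

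The 3 to 18 escalation range, the 42 maximum and the enrolment cap of 70 are unchanged. A reader might infer that patients are put at risk or that the response analysis is compromised. The documents do not support that; the effect is confined to stated planning numbers.

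**What to change.** Reconcile section 6.2.2 with section 12.1. The sponsor must first say which was intended.

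**If the rules stand as written**, change section 12.1, and the Trial Summary for the total:

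- No DLT: 6 escalation patients.
- One DLT at each opened level: 12.
- Maximum: keep 18, and describe its path (level 1 at 1/6; level 2 filled to six with two or more DLTs; level 2a filled to six).
- Total: 30 to 42 patients treated if the expansion is completed, before any added enrolment for non-evaluable escalation patients under section 6.7.1.
- State separately that a stop at level 1 treats 3 to 6, and that a safety halt could end the expansion below 24.

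**If six patients at the RP2D level were intended**, section 6.2.2 must say so. The no-DLT figure is then 9 and the total with a completed expansion is 33 to 42. The corrections to the scenario for 18 and to the 27 are still needed.

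The cost is a few sentences in section 12.1 and one in the synopsis, plus one in section 6.2.2 under the second option. The 18, 42 and 70 do not change, and under the rules as written no patients are added.

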3.3 Exploratory Objective

Objective: Evaluate the effect of the combination on the immune profile in the serum and in tumor biopsies.

Hypothesis: The IL-6 inhibitor will change the micro-environment to favor an immune response to the PD-1 inhibitor.

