5.4.1 Rationale for Endpoints

5.4.1.1 Efficacy Endpoints: This is a phase I trial. The primary endpoint is still toxicity. The plan is to evaluate the response rate, response duration, and progression free survival

Protocol/Version No.: 5, Date December 15, 2022

of the patients on the trial. These endpoints will provide preliminary data in advanced pancreatic cancer.

5.4.1.2 **Biomarker Research:** We intend in all patients to evaluate the effects of the combination on T-cell population in peripheral blood. In addition, we plan to evaluate the effects of the combination versus spartalizumab alone in paired biopsy samples. These samples will be analyzed for tumor infiltrating lymphocytes, stromal/tumor markers and expression immune inhibitory molecules (PD-L1, PD-L2, PD1, etc). We anticipate to see a difference between the groups treated with the combination versus the group treated with spartalizumab alone.

Table 4.0 Objectives and related endpoints

Objective	Endpoint	Analysis
Primary		Section 6.2
Evaluate the safety profile of the combination of siltuximab and spartalizumab	Determine the recommended phase II dose of siltuximab that can be combined with spartalizumab	
Key secondary		Section 14.3
To evaluate the activity of siltuximab and spartalizumab	Overall response rate (CR+ PR) in patients treated with siltuximab and spartalizumab	
Other secondary		Section 14.3
To evaluate the response duration, progression free survival and overall survival of patients with pancreatic cancer receiving siltuximab and spartalizumab	Response duration. progression free survival and overall survival time from treatment start until progression or death	
Exploratory		Section 7.1
Evaluate the effect of the combination on the immune profile in the serum and in tumor biopsies.	Characterization of immune cell phenotypes in serum and tissue pre and post treatment. Characterization of the effects of the combination on immune inhibitory pathways	
	Paul. 11 11 11 11 11 11 11 11	

Protocol/Version No.: 5, Date December 15, 2022

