f. HBV-DNA, Hepatitis B surface antigen (HBsAg), Hepatitis B core antibody (HBcAb), Hepatitis B surface antibody (HBsAb), HCV RNA- PCR

- g. Baseline imaging with 8 weeks of day 1 is acceptable
- h. Scans will be done every 3 cycles between day 15 and day 21 of that cycle
- i. Paired biopsies will only be obtained from patients on the dose expansion cohort at baseline and between days 14 and 21 of cycle 1. Archival tissue will be tested for MSI status.
- j. Samples will be collected at baseline, cycle1 days 1,8,15, cycle 2 day 1 and cycle 3 day 1. Blood will also be collected at EOT and disease progression. Analysis will include proportion of T, B, NK, memory and effector T cell subsets and expression of PD-1, PD-L1 and B7 family members.

Protocol/Version No.: 5, Date December 15, 2022

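### Section 5.4.1.2 plans a combination-versus-spartalizumab biopsy comparison that Section 12.1 says is not planned; the PI assigns the cycle 1 regimen by no stated rule, so the contrast, if made, is open to selection bias

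*Combined protocol and SAP*

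**What the plan says.** Section 12.1 (Determination of Sample Size) describes the expansion phase: "Patients in the expansion phase will be assigned to treatment arms by PI (spartalizumab or spartalizumab plus siltuximab"). It continues "After the first 3 weeks all patients will receive the combination therapy" and then "There is no planned comparison between the two arms".

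Section 5.4.1.2 (Biomarker Research) says "we plan to evaluate the effects of the combination versus spartalizumab alone in paired biopsy samples", and then "We anticipate to see a difference between the groups treated with the combination versus the group treated with spartalizumab alone".

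The exploratory objective in Section 3.3 is to "Evaluate the effect of the combination on the immune profile in the serum and in tumor biopsies". Its endpoint in Table 4.0 includes "Characterization of immune cell phenotypes in serum and tissue pre and post treatment".

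The timing is in the footnotes to the flow chart (Section 7.1): "Paired biopsies will only be obtained from patients on the dose expansion cohort at baseline and between days 14 and 21 of cycle 1". Section 6.3.5 makes the trial open label. Section 12.2 describes all analyses as hypothesis generating, without formal testing, but allows exploratory tests.

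**The concern.** An analyst cannot follow both sections: one plans a between-group evaluation of tissue and expects a difference, the other says the arms are not compared.

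The conflict matters because of how the groups arise. The PI decides, unblinded, who starts on spartalizumab alone and who starts on both drugs. Suppose that choice is related to anything that predicts how the tumor immune profile changes over three weeks, such as disease pace, biopsy site or fitness. A difference between the groups would then partly reflect who was chosen. At stake is whether a tissue difference in this trial can be read as an effect of adding siltuximab. Section 12.1 says the biopsies are meant to help develop the combination further.

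**Working it through.** **1. The two statements.** Section 5.4.1.2 names the contrast (combination versus spartalizumab alone), the material (paired biopsies) and the expected result (a difference). Section 12.1 rules out a comparison between the same two groups and does not limit this to efficacy or to formal testing. As worded, they conflict.

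**2. The assignment rule.** Four places describe the cycle 1 regimen.
- Section 12.1: the PI assigns one of two regimens.
- Section 8.1.1.1: patients who sign the optional biopsy consent are assigned to one of two starts; it does not say how.
- Section 8.1.3: siltuximab may be held in cycle 1 in selected patients having paired biopsies; no selection criterion.
- Section 7.1, footnote c: cycle 1 of the expansion phase is an exception to giving both drugs on day 1; no further detail.

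None gives a random list, alternation, ratio or criterion. The schema figure and the consent pages are not available, so this holds for the readable text only.

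**3. Timing.** The second biopsy is taken between days 14 and 21 of cycle 1, and everyone moves to the combination after the first three weeks. The biopsy therefore falls in the only period when the regimens differ, and the PI's choice fixes which regimen each tissue pair reflects. Pairing removes stable differences in baseline level. It does not remove differences between the groups in expected change.

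**4. Size.** There is no figure in the plan to reproduce. The 24 patients are justified by a response rate (alpha 0.1, power 90%, 20% against less than 5%), not by the biopsy contrast. The documents give no group sizes, SD or imbalance for the contrast and plan no such test or interval. The following is illustration only.

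Assumptions: n evaluable pairs per group, equal SD of the post-minus-pre change, no true regimen effect, and an imbalance of d SD in expected change caused by selection.
- CI half-width in SD units = t(0.975, 2n−2) × √(2/n).
- Chance that the 95% CI excludes zero = P(|T| > t(0.975, 2n−2)), where T is non-central t with 2n−2 df and non-centrality d × √(n/2).

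Half-widths:
- n = 12: 2.074 × √(2/12) = 0.85 SD.
- n = 6: 2.228 × √(2/6) = 1.29 SD.

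| Imbalance d (SD) | Non-centrality, n = 12 | CI excludes zero, n = 12 | Non-centrality, n = 6 | CI excludes zero, n = 6 |
|---|---|---|---|---|
| 0.1 | 0.245 | 5.6% | 0.173 | 5.3% |
| 0.3 | 0.735 | 10.8% | 0.520 | 7.6% |
| 0.5 | 1.225 | 21.6% | 0.866 | 12.3% |
| 0.8 | 1.960 | 46.6% | 1.386 | 24.1% |

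The nominal rate is 5%. The result is driven by d, on which the documents are silent.

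**5. Related wording.** On who is biopsied, Sections 2.0 and 6.1.1 and the opening of 8.1.1.1 describe paired biopsies for all expansion patients. Section 8.1.1, Table 10 and the consent sentence in 8.1.1.1 make them optional. On the cycle 1 regimen, footnote c, Section 8.1.3 and the two-start wording of 8.1.1.1 and 12.1 could describe one lead-in at different levels of detail, but they do not settle who receives what.

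**The case against.** The strongest reply is that the contrast is exploratory, that Section 12.2 plans no formal testing, and that Section 12.1 disclaims any comparison. Because that disclaimer stands in the sample-size section, it may mean only that no powered comparison is planned. With about 12 pairs per group or fewer, the interval is so wide that randomising might add little. Much of this stands: it limits the scope and makes a wording-only remedy reasonable. It does not remove the conflict. The disclaimer carries no such limit, Section 5.4.1.2 still announces a between-group evaluation, and Section 12.2 leaves room for exploratory tests.

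A reader might also infer more than the documents support:
- **A fixed false-positive rate.** The percentages above should not be read as properties of this trial. Nothing in the documents supports any particular imbalance.
- **A biased combination-only pre/post change.** No passage plans pre/post change reported separately by regimen. An uncontrolled change also depends on who is enrolled and on drift over time, whoever assigns the regimen.
- **A three-way conflict over biopsies.** The sentence in Section 2.0 about all patients follows directly on the description of the expansion phase and in context agrees with 6.1.1 and 8.1.1.1. What remains is all expansion patients versus optional.
- **Damage to the main result.** The RP2D objective does not use this contrast.

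Nor is a pooled pre/post biopsy change free of the problem. It mixes two regimens in an unstated ratio, so it depends on the split if the regimens differ.

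**Conclusion.** The point holds in a limited form. Sections 5.4.1.2 and 12.1 conflict on whether the two cycle 1 groups are compared in tissue. In the text available, the PI forms those groups open label with no stated rule, and the second biopsy is taken while their regimens differ. If the contrast is made, selection bias is not excluded and a difference could not be attributed to siltuximab.

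The size is unknown. Under the stated assumptions it runs from almost nothing (5.6% against a nominal 5%, for 0.1 SD and 12 per group) to serious (46.6%, for 0.8 SD). The half-widths of 0.85 to 1.29 SD mean that the contrast would be imprecise even without bias. Confidence is high on the textual conflict and lower on the absence of an allocation rule, since one could be in material not shown.

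**What to change.** Take one position and state it in both Section 5.4.1.2 and Section 12.1.

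- **If the contrast is wanted:** in 12.1, replace assignment by the PI with random allocation of the existing cycle 1 lead-in, from a pre-generated list held outside the clinical team. Report the between-group difference in post-minus-pre change descriptively with a 95% CI. Give the numbers allocated, biopsied and evaluable per group, because randomisation does not correct for optional or unevaluable biopsies. Cost: a list, a likely protocol and consent amendment, and loss of PI discretion over cycle 1. It adds no patients, visits or biopsies.
- **If it is not wanted:** remove the between-group statements from 5.4.1.2, or label the contrast non-randomised and not attributable to siltuximab. Report biopsy changes by regimen received without comparing them. Cost: wording only.

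Either way, reconcile whether expansion biopsies are for all patients (Sections 2.0, 6.1.1, 8.1.1.1) or optional (Section 8.1.1, Table 10, Section 8.1.1.1). Also reconcile the cycle 1 regimen wording in Section 7.1 footnote c and Sections 8.1.1.1, 8.1.3 and 12.1. Which regimen applies to whom is for the sponsor to state.

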6.7.1 Replacement policy

Escalation part:

Patients will not be replaced on study. However, if a patient is considered as non-evaluable for the DDS, enrollment of a new patient to the current cohort will be considered if there is less than the required number of evaluable patients. Enrollment of new patients may be considered until at least the minimum number (1 or 3) or at most the maximum number (3 or 6) of evaluable patients is achieved within the cohort. Minimum and maximum numbers of evaluable patients per cohort are defined in Section 6.2.2.

Expansion part:

During the dose expansion part, no replacements will be needed.

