Early stopping for safety: If we observe more than 3 dose limiting toxicities as defined in Section 6.3.2 and Table 7 (excluding death since a single death will fulfil the stopping rule) during the first 8 weeks of treatment in the first 12 patients in the expansion cohort, study enrollment be halted pending a safety review by the safety monitoring committee for a single death. Consideration for lower dose regimen will be discussed with DSMC and sponsors. If the plan is to test additional dose levels, the protocol and informed consent will be amended and re-submitted for review by the IRB.

The total number of patients who will undergo treatment will range from 27 to 42 patients. In order to have 42 patients undergo treatment, we plan to enroll up to 70 patients to account for screen failures.

Product: Siltuximab and Spartalizumab

Protocol/Version No.: 5, Date December 15, 2022

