12.3 Analysis Sets

All subjects who receive any amount of study drug will be included in the evaluation of safety and efficacy, except for patients who take less than 80% of their prescribed dose of siltuximab and spartalizumab since they will be considered in-evaluable for the primary endpoint of toxicity.

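### The expansion halt rule counts the first 12 patients whether or not they received both drugs or were observed for the window, so early DLT-free leavers lower the chance of halting, by an amount the documents do not fix

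*Combined protocol and SAP*

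**What the plan says.** The rule is in Section 12.1, under early stopping for safety. Its trigger is "If we observe more than 3 dose limiting toxicities", counted "during the first 8 weeks of treatment in the first 12 patients in the expansion cohort". Death is handled separately: "excluding death since a single death will fulfil the stopping rule". The result is a halt to enrolment pending a safety review. The rule states no target DLT rate, halting probability or error rate.

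Two other provisions decide who fills the 12 places.

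- Section 6.2.2 defines evaluability for escalation: "Patient will be considered evaluable for dose escalation decision if patients have received at least 2 infusions of" both drugs and "had safety assessments for a minimum of 6 weeks or have had a DLT during the first 6 weeks". Nothing extends this to expansion.
- Section 6.7.1 allows a further patient to be enrolled in escalation when one is non-evaluable. For expansion it says: "During the dose expansion part, no replacements will be needed".

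Section 12.3 has one more evaluability provision. It includes all treated subjects in the safety and efficacy evaluation, "except for patients who take less than 80% of their prescribed dose of siltuximab and spartalizumab since they will be considered in-evaluable" for the toxicity endpoint. That is a dose criterion for an analysis set, and it is not linked to the halt rule.

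Under Sections 8.1.1.1 and 12.1, some expansion patients receive spartalizumab alone in cycle 1. All patients move to the combination after the first 3 weeks.

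**The concern.** The rule compares a count with a fixed 12 places. A patient who leaves before the window ends, for a non-toxic reason and without a DLT, takes one of those places and adds nothing to the count. Exposure or observation that did not happen is treated as safe. A patient in the spartalizumab-alone group who leaves during cycle 1 has never received the combination, yet counts as a DLT-free place in the rule that guards against combination toxicity.

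Escalation avoids this through its evaluability definition and its provision for further enrolment. Expansion has neither, although Section 12.1 gives its aim as confirming safety and tolerability. At stake is the chance that the halt fires when the regimen is too toxic.

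**Working it through.** **No figure to reproduce.** The plan states no operating characteristic for this rule, so the check computes them.

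**Inputs**
- Trigger: 4 or more, from more than 3 (Section 12.1). The text counts toxicities, not patients; one DLT per patient is assumed.
- Places: 12 (Section 12.1).
- True 8-week DLT rate p: 33%, close to the one-third limit in the MTD definition (Section 2.0, which uses 6 weeks), with 40% and 20% for comparison.
- Fraction d lost to observation before week 8: not in the documents. Assumed 5% to 10%, with 25% as a pessimistic value.
- Loss and DLT onset are assumed even over the window, so a lost patient shows half of the window's risk.

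**Full observation.** P(halt) = P(X ≥ 4), X ~ Binomial(12, p). This gives 0.205 at p = 20%, 0.597 at 33% and 0.775 at 40%.

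**Rule as written.** Observable rate = p(1 − d) + p·d·0.5 = p(1 − d/2).

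| True p | d | Observable rate | P(halt) |
|---|---|---|---|
| 33% | 5% | 0.33 × 0.975 = 0.322 | 0.57 |
| 33% | 10% | 0.33 × 0.95 = 0.314 | 0.55 |
| 33% | 25% | 0.33 × 0.875 = 0.289 | 0.47 |
| 40% | 10% | 0.40 × 0.95 = 0.380 | 0.73 |
| 40% | 25% | 0.40 × 0.875 = 0.350 | 0.65 |
| 20% | 25% | 0.20 × 0.875 = 0.175 | 0.14 |

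A second model, with constant competing hazards for DLT and leaving, gives 0.551 at d = 10% and 0.475 at d = 25% for p = 33%. If 2 of the 12 contribute no observation at all, P(X ≥ 4) with X ~ Binomial(10, 0.33) is 0.432. Treating every leaver as wholly unobserved bounds the loss from above.

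**Rule restricted to evaluable patients.** A patient is evaluable with a DLT in the window, or on completing it. The DLT rate among evaluable patients is p(1 − d/2) / [p(1 − d/2) + (1 − p)(1 − d)].

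- p = 33%, d = 25%: 0.28875 / (0.28875 + 0.5025) = 0.365, so P(halt) = 0.69.
- p = 20%, d = 25%: 0.175 / (0.175 + 0.600) = 0.226, so P(halt) = 0.28.
- d = 5% to 10%: P(halt) is 0.61–0.63 at p = 33% and 0.22–0.23 at p = 20%.

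The restriction therefore overshoots full observation, because it drops only leavers without a DLT.

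**When the look is reached.** At p = 33% and d = 25% the evaluable fraction is 0.791, and 12 / 0.791 = 15.2, so the 12th evaluable patient is about the 15th or 16th enrolled. At d = 10% it is about the 13th (12 / 0.9165 = 13.1).

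**The case against.** The strongest reply is that leaving treatment is not leaving observation. Section 6.7 says patients who discontinue a drug are not withdrawn from the study. Section 6.7.3 follows all patients for safety to 150 days after the last dose, and suspected AEs are still collected after new anticancer therapy starts. A DLT must be at least possibly related (Section 6.2.3), so suspected AEs are the relevant ones. Withdrawal of consent (Section 6.7.2) and loss to follow-up (Section 6.7.6) end observation; a patient who stops for progression or intercurrent illness mainly loses exposure. Table 7 also makes any AE leading to permanent discontinuation a DLT, and one death meets the rule by itself. All of this stands, and it is why 25% is treated as pessimistic.

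A second reply is that Section 12.3 already removes under-dosed patients. It does not close the gap: it concerns dose, it is not linked to the halt rule, and it provides no further patient. Applied without refilling the place, it leaves fewer than 12 patients facing the same threshold of 4, and P(halt) still falls.

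A third is that the first 12 patients plainly means the first 12 evaluable ones. That reading would remove the problem, but the text does not say it, and the protocol spells out evaluability where it wants it.

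Finally, the study team also reviews all AE and SAE logs at its meetings (Section 11.0). That limits the consequence without repairing the rule.

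**Conclusion.** The point holds as a gap in the rule's definition. DLT-free early leavers fill places and lower the chance of halting in every case computed at a given true DLT rate. The size is uncertain: at a true 33% DLT rate, P(halt) falls from 0.60 to 0.57–0.55 if 5% to 10% are lost to observation, and to 0.47 under the pessimistic 25%. These figures rest on assumed loss rates, even timing and one DLT per patient. They do not model the lost exposure of patients who stop drug but remain in follow-up.

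A reader might infer that the rule misses a sensitivity the plan promises. The documents do not support that: none is stated, and the resemblance of 4 in 12 to the one-third MTD limit is the reader's own, since that limit uses 6 weeks and this rule 8. Nor do they support treating every early stop as unobserved, given the 150-day follow-up and the DLT status of AE discontinuations. This is a cheap improvement to a safety rule, not evidence that the rule fails.

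**What to change.** In Section 12.1, apply the rule to the first 12 DLT-evaluable expansion patients in order of enrolment: those with a DLT in the window, or those who completed the window with the required infusions of both drugs and the safety assessments. Count every DLT as it occurs, so that the halt can fire before 12 patients are evaluable. List DLT-free leavers separately.

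Reconcile three things in the same edit.

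- The evaluability definition with the 80%-dose rule in Section 12.3, so that there are not two unconnected definitions.
- The 8-week window with the 6-week DLT window in Section 6.2.3. This affects the infusion count: a lead-in patient's second siltuximab infusion is scheduled for cycle 3 day 1, which is day 43 (2 × 21 + 1). That lies inside 8 weeks (56 days) but outside 6 weeks (42 days).
- The cross-reference to Section 6.3.2, since the DLT definition is in Section 6.2.3.

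The cost is wording, with no added patients within the planned 24. Two downsides should be stated in the plan. The 12-patient look comes later, at about the 13th patient with 10% lost and the 15th or 16th with 25%. The rule also becomes somewhat conservative: at 25% leaving, P(halt) is about 0.69 at a true 33% and 0.28 at a true 20%, against 0.60 and 0.205 with full observation. At 5% to 10% the overshoot is small.
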